3.1.4. Consent Procedures

Once a patient is referred for enrollment for this study, only the anesthesiologists listed on this study ([name], [name], [name], [name] & [name]) will interview the patient to confirm that the minimum criteria listed in Table 2 are met. This interview will take place as soon as possible after the Pain Medicine physician-on-call refers the patient to the PI or SI. In all cases, this initial consultation will take place within 24 hours of the referral as is the standard practice for all consultation requests sent to the Pain Medicine physician-on-call. In the rare case that neither the PI nor any SI is available within this period,

the patient's PDPH will be treated according to standard practice. In no instance will treatment for PDPH be delayed because of failure of the PI or SI to interview the patient.

Only the anesthesiologists listed in this study will obtain informed consent ([name], [name], [name], [name] & [name]). The administrative assistant ([name]) will not obtain informed consent. Resident anesthesiologists will not obtain informed consent. Each patient will be given the informed consent document to read and consider prior to agreeing to participate. The PI or SI will answer all the subjects' questions and ensure the subject has had adequate time to consider participation prior to signing the informed consent document. No study assessments, measurements, or interventions will occur prior to subject signing the informed consent document. In addition, at each new encounter with the subject, the investigator will ask the subject if he or she is agreeable to continued study participation.

We acknowledge that due to the intensity of the headache and any associated symptoms, the patient may not be able to give informed consent to participate in this study. If the PI or SI determines in such a case that the patient's overwhelming symptomatology prevents decision-making capacity regarding participating in this study or if the patient states that he or she cannot make a decision regarding participation in this study, then the patient will NOT be enrolled in this study. No surrogate decision maker will be allowed to give consent. As noted earlier, such patients will be treated for their headache symptoms according to standard clinical practices taking the patient's wishes into consideration. Failure to consent for participation in this study will not in any way prevent a patient with PDPH from receiving the treatment he or she would have otherwise received.

3.1.5. Subject Costs and Compensation

The subject will not incur additional costs outside of standard of care costs for medication and pregnancy testing that may be performed for routine standard of care. There will be no compensation for participation in this study.

3.1.6. Chart Review Selection

There will be no retrospective chart review. Below is the "Data Collection List" that will be used to gather data at every patient encounter as described previously.

Data collection sheet

(3.1.6 : there will be no retrospective chart review)

GROUP 1:Epidural Blood Patch					
Subject ID:	0 mins VAS	30 mins VAS	60 mins VAS	24 hrs VAS	48 hrs VAS
Orthostatic HA					
Supine HA					
Nuchal HA					
Nausea					
Auditory Disturbances					
Visual Disturbances					
Vomiting					
Pruritis					
Epistaxis					
Numbness					
Comfort with Procedure					
Blood Pressure					
Heart Rate					
Allergies					

GROUP 2: SPG Block							
Subject ID:	0 mins VAS	30 mins VAS	VAS not improved, SPG 2 at 30 mins	VAS not improved, SPG 3 at 30 mins	60 mins VAS	24 hrs VAS	48 hrs VAS
Orthostatic HA							
Supine HA							
Nuchal HA							
Nausea							
Auditory Disturbances							
Visual Disturbances							
Vomiting							
Pruritus							
Epistaxis							
Numbness							
Comfort with Procedure							
Blood Pressure							
Heart Rate							
Allergies							

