1.0 Research Introduction

Title of Project

A Comparison of the Efficacy of Sphenopalatine Ganglion Block (SPGB) with 5% Lidocaine and Epidural Blood Patch (EBP) for the Treatment of Post-Dural Puncture Headache (PDPH)

NCT# 03112720

Principal Investigator

[name], DDS

Sub-Investigators

[name] MD, [name] MD, [name] MD, [name] MD
(Administrative Assistant)

Funding Source

Department of Anesthesiology

1. Purpose

To compare the sphenopalatine ganglion block (SPGB), a local anesthetic technique that is facile to perform and carries fewer potential side effects, to the traditional, more invasive, epidural blood patch (EBP) for the treatment of post-dural puncture headache (PDPH). The SPGB is experimental while the EBP is considered to be the standard of care.

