Although the EBP has been proven to be one effective treatment for PDPH, it is an invasive procedure and carries the same risks as those associated with the inciting event. Infections, subdural and epidural hematoma, needle trauma, and back pain have been described (10,11), in addition to a possible second dural puncture. Furthermore, the procedure requires the physician to be adept at the epidural injection technique, which usually limits treatment to anesthesiologists.

Given the purported neurovascular etiology of PDPHs, patients who suffer from this condition have been successfully treated with nerve blocks for immediate relief (12). We had proposed targeting the sphenopalatine ganglion based on the success of manipulating the trigeminal-autonomic arc for treating cluster headache, a type of neurovascular headache. Briefly, this reflex arc describes an afferent limb that includes trigeminal nerve fibers in the perivascular area of cerebral circulation. When stimulated, these neurons activate the efferent limb, the parasympathetic fibers within the greater superficial petrosal nerve, which in turn causes vasodilation (13). In neurovascular headaches, a triggering mechanism causes initial vasodilation which irritates the dura and stimulates the afferent limb of this arc. In PDPH, the equalization of pressure between the CSF and the atmosphere acts as a trigger. The parasympathetic efferent limb of this reflex causes vasodilation, which in this case is deleterious since it provides positive feedback to this reflex loop, causing continued headache. Blockade of the synaptic communication in the SPG would terminate this loop, and is the proposed pathophysiological mechanism by which neurovascular headaches are treated.

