3.3.3. EBP

Immediately after obtaining informed consent, inclusion in the study, transport to the OR holding suite, randomization to the control arm of this study, completion of the time-out procedure, and initial symptom assessment, the patient will receive an EBP. The EBP involves three separate procedures: epidural access, venipuncture, and autologous transfer. Vital-sign monitoring of the patient as described above will commence once the patient is checked into this area. Symptom assessment will be as described in section 3.2.3. In addition, the investigator will assess whether the patient has any adverse effects of this procedure. These are rare, but could include pain at the site, a new motor deficit, a new sensory deficit and continued bleeding from any puncture site.

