5.2. Analysis

Nonparametric data such as those resulting from the VAS assessments from the two groups will be compared using the Mann–Whitney U test. The Student's *t*-test will be used to compare normally distributed continuous variables. A *p* value of less than or equal to 0.05 will be considered statistically significant.

6. Data and Safety Monitoring

All subjects enrolled in this study will receive at least one of two types of treatment for their PDPH. Both the EBP and SPG block are low-risk procedures that can be and are routinely performed in an office setting on outpatients in our pain clinic at the New Jersey Pain Institute. Furthermore, neither of these techniques are experimental; rather, their methods are well documented in literature and are common procedures in the pain medicine field.

Subjects who undergo the procedures within this study will have additional monitoring as opposed to patients who undergo the same procedures outside of this study. Patients in this study will receive two follow-up phone calls to assess their symptoms and to expedite the availability of any additional procedures that need to be performed. These telephone calls will also serve to inform the SIs and PI if the patients are experiencing any undue and unexpected harms as a result of this study. As all of the investigators in this study are in the department of anesthesia, they are the best equipped to identify potential side effects and treatment.

All subjects enrolled in this study will be given a contact sheet including phone numbers by which they may reach the PI, emergency room, the pain clinic, and the Pain Medicine

physician-on-call who, as previously stated, is available continuously by mobile telephone.

7. Reporting Results

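### The data sheet has no adverse-event field, and a row for only one of the four EBP harms named in the procedure section (two of four for SPGB), so EBP harms risk being recorded less completely

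*Combined protocol and SAP*

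**What the plan says.** Section 1 (Purpose) introduces SPGB as "a local anesthetic technique that is facile to perform and carries fewer potential side effects", in contrast to the more invasive EBP.

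Section 3.1.6 gives one data sheet per arm, "that will be used to gather data at every patient encounter as described previously". Both sheets have the same 14 rows: three headache types, nausea, auditory and visual disturbances, vomiting, pruritus, epistaxis, numbness, comfort with the procedure, blood pressure, heart rate and allergies. The EBP sheet has columns for 0, 30 and 60 min, 24 h and 48 h. The SPGB sheet adds two columns for repeat blocks.

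Section 3.3.3 says EBP adverse effects "could include pain at the site, a new motor deficit, a new sensory deficit and continued bleeding from any puncture site". Section 2 (Background and Significance) adds, for EBP: "Infections, subdural and epidural hematoma, needle trauma, and back pain have been described (10,11), in addition to a possible second dural puncture". Section 3.3.4 names four effects for SPGB: nasal pain, epistaxis, numbness of the pharynx and a bitter taste. Sections 3.3.3 and 3.3.4 both instruct the investigator to assess adverse effects in addition to the symptom assessment.

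Section 3.2.3 specifies the 24 h and 48 h contacts as the Table 8 symptoms, in person or by telephone. Section 6 (Data and Safety Monitoring) adds that the calls will tell the investigators "if the patients are experiencing any undue and unexpected harms as a result of this study".

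**The concern.** The form asks directly about some harms typical of SPGB and hardly any typical of EBP. A patient with site pain or new leg weakness the day after an EBP has no row on the printed sheet, whereas a nosebleed has its own row at every assessment. Solicited events are usually captured more completely than those left to spontaneous report or to an unstructured question. The gap matters most here because the trial is open-label, the EBP assessments at 30 and 60 min are made by the anesthesiologist who did the procedure, and discharged patients are followed by telephone, where weakness or bleeding is found only if someone asks.

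At stake is the trial's ability to say anything about relative side effects, which its stated purpose takes as a premise.

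**Working it through.** The plan gives no figure to reproduce, so the check sets the named harms against the sheet rows, using the Table 8 definitions.

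**Step 1. Harms named in the two procedure sections.**

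| Procedure | Named harm | Nearest row | Recordable? |
|---|---|---|---|
| EBP (3.3.3) | Site pain | None; nuchal headache is neck pain, and comfort concerns the procedure itself | No |
| EBP | New motor deficit | None | No |
| EBP | New sensory deficit | Numbness | Yes |
| EBP | Continued puncture-site bleeding | None; epistaxis is nasal only | No |
| SPGB (3.3.4) | Nasal pain | None | No |
| SPGB | Epistaxis | Epistaxis | Yes |
| SPGB | Pharyngeal numbness | Numbness | Yes |
| SPGB | Bitter taste | None | No |

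EBP: 1 of 4. SPGB: 2 of 4. The difference is one item.

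**Step 2. EBP harms named only in the background.** Section 2 lists six: infection, subdural hematoma, epidural hematoma, needle trauma, back pain and second dural puncture. None has a row (0 of 6). Pooled with Step 1 this is (1 + 0) of (4 + 6) = 1 of 10, or 1 of 9 if site pain and back pain are treated as one. This is context only. It should not be set against 2 of 4, because the SPGB count uses the procedure section alone.

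**Step 3. Other routes by which a harm could be recorded.**

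- *Adverse-effect assessment (3.3.3, 3.3.4).* Required in both arms, in the same terms. Neither section gives an explicit time point, a grading or a field for the result, and the sheet has no line for it.
- *24 h and 48 h contacts (3.2.3, Section 6).* Specified as Table 8 plus undue and unexpected harms. Section 4.3 describes the procedures' own risks as not specific to study participation. On a narrow reading, a known EBP complication is neither a Table 8 symptom nor an unexpected harm of the study.
- *Attachment 1 (4.2).* A questionnaire for the Section 3.2.3 symptom assessment. It is not in the text available, so further harm items can be neither confirmed nor excluded.

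**Step 4. Where EBP harms can arise.** Under Section 3.2.3, a patient whose third SPGB fails may be offered an EBP, and patients in either arm whose symptoms return may choose either procedure. EBP harms can therefore occur in the SPGB arm, and a count by randomised arm alone would not show which procedure caused them.

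**Step 5. Direction.** Missed EBP harms make EBP look safer. Any distortion would work against SPGB, and so against the trial's own premise.

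**The case against.** The strongest reply is that harms are assessed. Sections 3.3.3 and 3.3.4 require it in both arms, and because the instruction follows directly on the symptom assessment, it can be read as applying at the same times. Section 6 uses the calls to detect harms and relies on investigators who are well placed to recognise side effects; reading its wording as excluding leg weakness after an EBP is strained. This stands to the extent that under-recording is a risk and not a demonstrated result. It does not supply a place to write the finding down.

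Second, Table 8 scores numbness with a location, so pharyngeal numbness and a limb deficit can be told apart. That stands, although the printed sheet has no location field.

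Third, the sheet is incomplete for SPGB too. It omits bitter taste, which Section 2 describes as the usual side effect. That also stands, and is why the like-for-like gap is one item. A reader might infer a much larger imbalance from 1 of 10 against 2 of 4. The documents do not support that contrast: the denominators come from different sections, some of the ten overlap, and hematoma and infection are diagnoses, not symptoms a patient would score.

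Fourth, no adverse-event comparison appears in the objectives (1.1), hypotheses (1.2) or analysis (5.2), and Section 3.6 defends the margin by the patients spared an invasive procedure, not by a difference in harm rates. This stands as well.

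**Conclusion.** The concern holds in a limited form. The sheet meant for every encounter has no adverse-event field and no row for three of the four EBP harms in Section 3.3.3, or for two of the four SPGB harms in Section 3.3.4. With no stated recording place or explicit schedule for the required adverse-effect assessment, EBP harms are at risk of less complete capture than SPGB harms: 1 of 4 against 2 of 4 have a row.

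The consequence is that the trial could say little about its premise that SPGB carries fewer side effects. The efficacy comparison is unaffected.

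A reader might go further and infer that EBP harm is in fact under-recorded, that a planned side-effect comparison is biased, or that the margin loses its justification. The documents support none of these: adverse effects must be assessed in both arms, no such comparison is planned, and the margin rests on another argument.

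The conclusion assumes that the printed sheet is the operative form and that Attachment 1 adds no harm items. If Attachment 1 does contain them, the gap narrows or closes.

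**What to change.** Add one identical adverse-event block to both sheets and to the 24 h and 48 h call script, asked at each post-procedure assessment in both arms:

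- back or site pain;
- new limb weakness;
- new sensory loss, with the location Table 8 already calls for;
- bleeding at any site;
- fever or suspected infection;
- nasal pain;
- bitter taste;
- free text for anything else.

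Have the operator record any recognised dural puncture once for each EBP performed, including an EBP given after a failed SPGB. It makes no sense to ask patients about it at every contact.

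State in Section 5.2 that counts will be tabulated descriptively by randomised arm and by procedure received. If Attachment 1 already has some of these items, align the sheet with it.

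The cost is a few extra form lines and slightly longer contacts, with no extra visits.

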3.2. Study Design

3.2.1. Type

This is a non-inferiority trial comparing the SPGB to the EBP for the treatment of PDPH. The study is not blinded to the subject or investigator. Due to the nature of the procedure and the anatomical site of intervention, both will know which method they are receiving or delivering. We acknowledge this as a limitation of our study but reiterate that blinding one or both parties is not feasible.

3.2.2. Randomization

Subjects suffering from PDPH shall be randomized to one of two groups (**Table 7**) by a random number generation spreadsheet (Excel, Microsoft, Redmond, Washington).

Table 7. Patients with PDPH to be treated for their symptoms are randomized to one of the two groups below

Group	Intervention
1, EBP (control)	EBP as described below
2, SPG block (treatment)	SPG block as described below

[figure not shown]

For patients randomized to group 2 (SPGB), the symptoms in Table 8 will be assessed and graded at 30 min post-procedure. If this treatment does not decrease the patient's "orthostatic headache" severity past the pre-treatment score, then the SPGB will be performed for a second time. The symptoms will be graded again 30 min after the second block. If the "orthostatic headache" severity score is still unchanged, then a SPGB will be performed for a third time. If the "orthostatic headache" severity score remains unchanged at the 30 min mark following the third SPGB, the procedure will be considered a failure and conservative measures or an EBP will be offered to the patient.

If the first, second or third SPGB succeeds in decreasing the "orthostatic headache" severity score at 30 min post-procedure, the symptoms in Table 8 will be assessed and graded again at 60 min post-procedure. In all cases, the same symptoms will be assessed at 24 and 48 hours post-procedure in the manner noted above. If patients in any group on telephone interview note dissatisfaction with the alleviation of the symptoms or if the symptoms return, they will be given the option of arriving at the Pain Clinic at the New Jersey Pain Institute during normal clinic hours or to the emergency room (ER) after hours. At that time, they will be given the option of an EBP, SPGB or medical management. This is the same as what would be offered if a patient underwent treatment for a PDPH outside of this study and had symptoms return afterward.

3.3. Procedures

3.3.1. Location

Both procedures, the EBP and the SPGB will take place in the Regional Nerve Block Area, a section of the operating room holding (OR holding) suite specifically designed for the performance of regional nerve blocks. Patients who consent to this study will be transported to this area by the institution's patient transport personnel and any other personnel that the institutional policy dictates. This area is accessible by anesthesiologists and includes the requisite monitoring and procedure equipment. This private area is the same location used by anesthesiologists for other regional nerve blocks; however, only one patient will be in any one bed location area at any given time.

Only the anesthesiologists ([name], [name], [name], [name] & [name]) will perform these procedures. Administrative assistants ([name]) and residents will not perform any procedures. Ancillary staff such as resident physicians, nurses and technicians may be required to assist in checking the patient into the area, monitoring, and positioning as institutional policy dictates. The pregnancy test is part of the exclusion criteria (section 3.1.3) and all details with respect to the pregnancy test can be found in that section. The pregnancy test is not a part of the procedures.

3.3.2. Monitoring

While either the EBP or SPG block are performed, the patient's vital signs will be monitored by continuous pulse oximetry and five-lead electrocardiography (EKG) and a non-invasive blood pressure cuff cycled at least every five minutes. After the randomized procedure is assigned, a time-out procedure will be performed according to institutional protocol.

3.3.3. EBP

Immediately after obtaining informed consent, inclusion in the study, transport to the OR holding suite, randomization to the control arm of this study, completion of the time-out procedure, and initial symptom assessment, the patient will receive an EBP. The EBP involves three separate procedures: epidural access, venipuncture, and autologous transfer. Vital-sign monitoring of the patient as described above will commence once the patient is checked into this area. Symptom assessment will be as described in section 3.2.3. In addition, the investigator will assess whether the patient has any adverse effects of this procedure. These are rare, but could include pain at the site, a new motor deficit, a new sensory deficit and continued bleeding from any puncture site.

3.3.3.1. Epidural Access

Epidural access will be performed by the anesthesiologist using the Perifix FX Epidural Anesthesia Kit (Braun, Bethlehem, Pennsylvania), the same kit that is currently used for epidural anesthesia. The subject will be

positioned in either the decubitus or sitting position. The anesthesiologist will wear sterile gown and gloves. The patients' skin over the lumbar area will be prepped with povidone-iodine three times and draped in a sterile fashion. The appropriate lumbar interspace, one or more interspaces above the presumed site of the initial dural puncture, will be identified by anatomical landmarks and palpation. Five mL of 2% lidocaine will be locally infiltrated with a 25-gauge needle. A 17-gauge Touhy needle will be placed into the epidural space using the loss-of-resistance to air technique. Once positioned, the sterile stylette will be replaced within the needle to maintain the sterility of the epidural space. All of the equipment described in this section is included in the aforementioned kit.

3.3.3.2. Venipuncture

A tourniquet will be applied to either upper extremity to identify a peripheral venous site. The intended area of venipuncture will be prepped with betadine or chlorhexidine gluconate and isopropyl alcohol 1-mL applicator (ChloraPrep, CareFusion, San Diego, California) according to the manufacturer's directions. Venipuncture will be performed with an 18-gauge needle attached to a 20-mL syringe. Twenty mL of blood will be aspirated into this sterile system. The tourniquet will be released and the needle, removed. Hemostasis will be achieved with manual pressure followed by a sterile dressing.

